8.3 Pharmacokinetics

Experimental arm: Sparse PK sampling for APR-246 will be done at all sites in cycles 1-3, on Days 1, 2 and 4.

For both arms, azacitidine PK will be done at selected sites in cycle 1, on Day 4.

Due to the instability of both drugs a strict routine for serum preparation and handling must be followed, as outlined in the Laboratory manual.

Table 9. Sparse PK Blood Sampling Time Points for APR-246 (first 3 cycles) and azacitidine (first cycle only)

Experimental Arm: PK for APR-246 (Cycles 1 – 3) at all sites, all patients¹

APR-246 Sample Time Points	D1	D2	D4
Prior to APR-246 infusion	×	×	×
At the end of APR-246 infusion	×		×
30 – 60 min after APR-246 infusion	×		× ¹

¹ Selected Sites Only: the sampling on Day 4 of the APR-246 infusion is coordinated with azacitidine sampling. Please see Laboratory Manual for sites participating in azacitidine PK sample collection: Section 1.2.3, Figure 4 (part C), and page 44 (PK Blood Sampling and Collection Form).

Experimental and Control Arms: PK for azacitidine (Cycle 1)

Azacitidine Sample Time Point	C1D4
Prior to azacitidine administration	×
At the end of azacitidine administration	×
0.25 hour after administration	×
0.5 hour after administration	×
1 hour after administration	×
2 hours after administration	×
4 hours after administration	×

8.4 ECG in Experimental Arm: ECG for APR-246

Table 10 describes the routine ECG requirements from screening through cycle 4:

Table 10. ECG Requirements in Experimental Arm

Time Point	ECG, number	Timing
Baseline/Screening	Triplicate	Must be within 28 days of C1D1
Cycle 1, Days 1-4	Triplicate	Pre-dose; Post dose (6 hrs. after start of infusion; ± 30 min)
Cycles 2+, Day 1	Triplicate	Pre-dose

If repeated QTcF measurements show a stable QTcF < 450 msec, or if QTcF remains stable within the interval of 450 – 469 msec with no significant change at the end of infusion during several cycles of treatment, reducing the number of ECGs performed in the study may be discussed with the Medical Monitor.

If a patient starts treatment with another medication known to prolong QT interval at any time during the study therapy, an additional pre- and post-dose (6 hours after start of infusion, ± 30 min) ECG should be performed on the next treatment day.

Please consult Section 6.2.1 for additional requirements for proceeding with treatment with APR-246.

8.5 TP53 Testing

Patients are enrolled based on central interpretation of local NGS *TP53* sequencing results confirming at least one *TP53* mutation not defined as benign or likely benign (see Laboratory Manual). Next-generation sequencing data report (de-identified, with only the patient's assigned screening number) must be sent to the central laboratory for evaluation of *TP53* data.

9.0 STATISTICS

9.1 Sample Size

This trial will include 154 patients with 77 patients randomized in a 1:1 ratio to each of the two treatment arms (APR-246 + azacitidine treatment versus azacitidine treatment alone).

If the true CR rate is 50% for the treatment arm and 25% for the control arm, the trial will have 90% power to detect a statistically significant effect in favor of the APR-246 at a 2-sided alpha = 0.05 significance level.

9.2 Analysis Populations

Intent-to-Treat (ITT) population: All patients who are randomized on study will be considered eligible for the ITT population and will be used for demographics, baseline characteristics summaries. The ITT population will be the primary analysis population for efficacy.

Efficacy-Evaluable (EE) population: All patients who complete at least one treatment cycle of APR-246 and azacitidine and who have at least one post-treatment clinical response assessment. Patients who fail to complete one post-treatment clinical response assessment will also be considered EE if they show clear evidence of clinically significant disease progression. The EE population will be the secondary analysis population for efficacy.

Safety population: Patients will be evaluable for safety if they receive at least one dose of APR-246 or azacitidine. The safety population will be used to summarize exposure and safety parameters.

Pharmacokinetics: Patients will be evaluable for pharmacokinetics if at least one sample for PK evaluation has been obtained.

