
Statistics
	
This study will be a multi-center, open-label, randomized, controlled Phase III trial to compare the efficacy of APR-246 in combination with azacitidine versus azacitidine alone for the treatment of TP53 mutant MDS.
 
Analysis Populations
 
Intent-to-treat (ITT): All patients who are randomized on study will be considered eligible for the ITT population and will be used for demographics, baseline characteristics summaries. The ITT population will be the primary analysis population for efficacy.
 
Efficacy evaluable (EE): All patients who complete at least one treatment cycle of APR-246 and azacitidine and who have at least one post-treatment clinical response assessment. Patients who fail to complete one treatment cycle will also be considered EE if they show clear evidence of clinically significant disease progression. The EE population will be the secondary analysis population for efficacy.
 
Safety population: Patients will be evaluable for safety if they receive at least one dose of APR-246 or azacitidine. The safety population will be used to summarize exposure and safety parameters.
 
Pharmacokinetics (PK): Patients will be evaluable for pharmacokinetics if at least one sample for PK evaluation has been obtained.
 
Determination of Sample Size
 
This trial assumes a sample size of 154 patients with 77 patients randomized in a 1:1 ratio to one of the two treatment arms (APR-246 + azacitidine treatment versus

azacitidine treatment alone). If the true CR rate is 50% for the treatment arm and 25% for the control arm, the trial will have 90% power to detect a statistically significant effect in favor of the APR-246 treatment combination at a 2-sided alpha = 0.05 significance level.

Efficacy Analyses

Primary endpoint CR will be summarized for all randomized patients (ITT) as the proportion of patients (%) with CR. CR will be compared between arms using a Cochran-Mantel-Haenszel (CMH) test stratified by age (< 65 years versus ≥ 65 years). In addition to presenting the CR rate and associated exact 95% confidence intervals (CI) for each treatment arm, the treatment effect will be described using the CMH estimate of the common odds ratio together with its associated 95% CI.

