6.0 TREATMENT OF SUBJECTS

6.1 Drug Preparation and Administration

At the pharmacies, the IMP vials are to be stored at 2-8°C (35.6-46.4°F). At the pharmacies and at the study centers, the prepared APR-246 study product (diluted in sodium chloride solution) is to be stored at not more than 25°C. The infusion should be completed within 24 hours from the time of preparation (see Pharmacy Binder).

APR-246 treatment (Experimental Arm only) will be administered on Days 1-4, and azacitidine on Days **4-10** (Figure 4). Treatment may be administered on an outpatient basis. No investigational or commercial agents or therapies other than those described below may be administered with the intent to treat the patient's disease.

Patients will be randomized (1:1) to 1 of 2 arms, Experimental or Control arm.

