6.4 Monitoring Subject Compliance

All instances of protocol deviations will be entered into Monitor Express and will be reviewed by the Investigator, Sponsor and appropriate Theradex designee.

Footnotes to Schedule of Study Evaluations

- a. All screening/baseline evaluations will be performed within 28 days prior to the start of APR-246 and azacitidine treatment. In the event that a visit or test cannot be scheduled on the exact visit day, a window of ± 3 days is allowable.
- b. A window of ± 3 days applies to this study visit.
- c. After the first cycle, Day 1 evaluations of subsequent cycles are to be done within 3 days prior to next cycle drug administration.
- d. Confirmation of TP53 status for eligibility will be performed centrally using the local lab report.
- e. Full medical history will be obtained at baseline for safety and eligibility purposes; this will include any issues/clinically significant findings from 28 days prior to screening date.
- f. Physical exam and vital signs (including blood pressure, heart rate, respiration rate and temperature) will be completed for safety purposes and clinically significant items will be recorded as AEs where appropriate. **In Experimental Arm, vital signs will be collected prior to APR-246, 2 hours into infusion and at end of infusion (EOI) (± 30 min. at all time points). Both arms: if azacitidine is given via IV infusion, vital signs will be taken before the infusion (within 0-2 hours) and at EOI (30-60 minutes); if azacitidine is given via SQ injection, vital signs will be taken before the injection (within 0-2 hours). In the Control Arm, the physical exam and vital signs are not needed on each day prior to the first day of azacitidine administration; vital signs will be assessed on treatment days only.**
- g. For Experimental Arm Only, APR-246 is administered IV on days 1-4 of each 28-day cycle.
- h. Azacitidine is administered SC over 7 consecutive days, on Days **4-10** of each 28-day cycle. On **Day 4** azacitidine is administered immediately after the APR-246 infusion. SC route is preferred but site may give IV at the investigator's discretion. The same route should be maintained over the 7-day treatment period (whichever route is used on day **4**, the other days should follow the same route of administration).

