7.5 End of Treatment Visit (All Patients)

This visit should take place within 28 days of the last dose of APR-246 or azacitidine, if treatment is stopped early for any reasons.

- Physical examination: weight, body surface area.
- Vital Signs
- Disease Assessment
- Bone marrow aspirate and biopsy core for exploratory objectives. If no aspirate is available, then peripheral blood is acceptable.
- ECOG performance status
- Hematology
- Blood chemistry
- Safety: Adverse events must be collected up to 30 days after the last dose.

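### The efficacy-evaluable definition cannot be met by the azacitidine-only arm as worded, and its progression exception differs between the synopsis and section 9.2

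*Combined protocol and SAP*

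**What the plan says.** The synopsis (Statistics, Analysis Populations) and section 9.2 share the same main criterion for EE: "All patients who complete at least one treatment cycle of APR-246 and azacitidine and who have at least one post-treatment clinical response assessment". Both name EE as the secondary efficacy population, after ITT.

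The progression exception is worded differently in the two places:

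- Synopsis: "Patients who fail to complete one treatment cycle will also be considered EE if they show clear evidence of clinically significant disease progression".
- Section 9.2: "Patients who fail to complete one post-treatment clinical response assessment will also be considered EE", again provided that there is clear, clinically significant progression.

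Section 6.1 states who receives the investigational drug: "APR-246 treatment (Experimental Arm only) will be administered on Days 1-4". Footnote g to the Schedule of Study Evaluations agrees: "For Experimental Arm Only, APR-246 is administered IV on days 1-4 of each 28-day cycle".

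Section 7.5 covers early stopping: "This visit should take place within 28 days of the last dose of APR-246 or azacitidine, if treatment is stopped early for any reasons". The procedures listed for that visit include "Disease Assessment".

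**The concern.** There are two separate faults in the rule for a named efficacy population.

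First, the main criterion requires a completed cycle of a drug that half the trial never receives. Followed literally, the control EE set could contain only patients admitted through the progression exception. A comparison between arms on that basis could not be interpreted.

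Second, the two exceptions waive different requirements, so EE membership depends on which page is followed. The patients in dispute have progressed and are therefore likely non-responders, so leaving them out shrinks the denominator of a response rate. The documents do not say who assigns EE status, or when. In an open-label trial that choice should be settled in writing before any EE output exists.

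**Working it through.** **Background figure.** Section 9.1 gives 77 per arm for CR rates of 50% and 25%, 90% power and two-sided alpha 0.05. The pooled normal approximation without continuity correction, with mean rate 0.375, gives

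n = [1.960 × √(2 × 0.375 × 0.625) + 1.282 × √(0.25 × 0.75 + 0.50 × 0.50)]² / 0.25² = (1.342 + 0.848)² / 0.0625 ≈ 76.7, so 77 per arm and 154 in total.

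Power at 77 per arm is 90.1%. The figure reproduces. It concerns ITT and is not in dispute.

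**Step 1: literal main criterion.** The inputs are the main criterion (synopsis and 9.2), APR-246 in the experimental arm only (6.1, footnote g) and 77 controls (9.1). No control can complete a cycle of both drugs, so 0 of 77 meet it. This restates the wording; it is not an effect on a result.

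**Step 2: the exceptions, with EE read as assigned treatment.** Let C = a completed cycle of assigned treatment, A = at least one post-treatment response assessment, and P = clear progression.

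- Main rule, both texts: C and A.
- Synopsis exception: not C, and P.
- Section 9.2 exception: not A, and P.

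| With P | Synopsis | Section 9.2 |
|---|---|---|
| C, A | EE | EE |
| not C, A | EE | not EE |
| C, not A | not EE | EE |
| not C, not A | EE | EE |

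Two of the four rows conflict. Without P, the row C and A is EE under both texts and the other three rows are EE under neither, so none of those four conflicts. Overall 2 of 8 conflict.

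**Step 3: does this depend on how broadly the exceptions are read?** The table treats each exception as sufficient on its own. Suppose instead that each waives only the requirement it names and the other must still be met. The last row then becomes not EE under both texts, and rows two and three are unchanged. As long as both texts are read the same way, the same two rows conflict.

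**Step 4: can a patient reach these rows?** A patient who stops during Cycle 1 because of progression is sent to the section 7.5 visit, which includes a disease assessment. If that counts as the response assessment, the patient is in row two: kept by the synopsis, dropped by section 9.2. If it does not count, the patient is in row four and the texts agree. The documents do not say which applies.

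**Step 5: possible effect, illustration only.** The count of 5 is assumed. Removing 5 non-responders from an arm of 77 leaves 72. An expected CR rate of 25% becomes 19.25/72 = 26.7%, and one of 50% becomes 38.5/72 = 53.5%.

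**Minor related point.** Section 9.3.3 opens the treatment-emergent adverse event window at a Day 1 infusion. Controls have none; section 7.4.1 starts their azacitidine on Day 4, usually 4 − 1 = 3 days later.

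**The case against.** The strongest reply concerns weight. EE is a supporting population: section 9.3.1 attaches no between-arm EE test to it, the primary analysis uses ITT, and no EE result is shown to be wrong. That is correct and limits the severity.

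The intended meaning of the main criterion is also fairly plain. Footnote a to the Schedule uses the same pairing for every patient: "All screening/baseline evaluations will be performed within 28 days prior to the start of APR-246 and azacitidine treatment". A reasonable reader would take the criterion as one cycle of assigned treatment. This too is fair, although the safety population in section 9.2 joins the two drugs with *or* and so fits both arms, and no passage supplies the assigned-treatment reading for EE.

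The conflicting rows are logical cells, not patient counts, and may be sparsely filled. Footnote r and sections 7.3.4 and 7.4.3 schedule a response assessment at the end of odd cycles too, so a patient who completes Cycle 1 is due one at once. The row with a complete cycle and no assessment therefore needs a missed assessment. The other row, reached by the early-stopping path, depends on how the End of Treatment assessment is counted.

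All of this bears on frequency. None of it reconciles the two exceptions. Both are current text and no rule of precedence is given.

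**Conclusion.** The concern holds, as something that should be fixed and not as a threat to the primary result. The main criterion is wrong as worded for the azacitidine-only arm. Separately, and in both arms, the two progression exceptions contradict each other in 2 of the 4 combinations a progressing patient can have. That count assumes EE is read as assigned treatment and both exceptions are read in the same way.

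The number of patients affected and any effect on an EE estimate cannot be derived from the documents. The ITT comparison of CR and its power do not change. The adverse event window is a small definitional gap: section 8.1.2.1 collects events in both arms from eligibility confirmation, so nothing is lost at collection.

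**What to change.** Put one identical EE definition in the synopsis and section 9.2:

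- **Main criterion:** at least one completed cycle of the assigned regimen (APR-246 plus azacitidine, or azacitidine alone) and at least one post-treatment response assessment. Say how to classify an experimental-arm patient who completes a cycle of only one of the two drugs.
- **Exception:** a single sentence naming what it waives. One option is that a patient who misses the completed cycle, the assessment, or both still counts as EE if there is clear evidence of clinically significant progression. The choice is the sponsor's; it needs to be the same in both places.
- **End of Treatment visit:** state whether the section 7.5 disease assessment counts as the post-treatment response assessment.

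As a minor change to section 9.3.3, start the treatment-emergent window at each patient's first dose of any assigned study drug and end it 30 days after the last dose. Do not fix calendar days by arm, because section 6.2.1 allows an APR-246 dose to be omitted.

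The cost is wording only, before any EE output is produced, with no new data. The example exception keeps both disputed groups, so EE could be slightly larger than under either current text. The safety window will usually open about 3 days later in controls, which should be noted when adverse event rates are compared.

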9.3 Statistical Methods

9.3.1 Efficacy Analyses

Primary endpoint CR will be summarized for all randomized patients (ITT) as the proportion of patients (%) with CR. CR will be compared between treatment arms using a Cochran-Mantel-Haenszel (CMH) test stratified by age (< 65 years versus ≥ 65 years). In addition to presenting the CR rate and associated exact 95% CI for each treatment arm, the treatment effect will be described using the CMH estimate of the common odds ratio together with its associated 95% CI.

Duration of response (DOR) is defined as the time from the date when criteria for

response) are met to the date of relapse, progression, or death due to any cause, whichever occurs first. Patients alive without relapse or progression will have their DOR censored at the date of the last clinical assessment. The duration of CR will be summarized in each treatment arm by providing the median DOR together with associated 95% CI, using Kaplan-Meier methodology.

Overall response will be summarized in number (%) of patients in each category of responses (CR, PR, mCR with HI, mCR without HI, HI). ORR will be analyzed by using the similar method as primary endpoint CR. DOR, as defined above, will also be evaluated in regards to ORR.

Time to AML is calculated from first day of study treatment to first onset of AML. Kaplan-Meier methodology will be utilized. Rate of AML transformation will be analyzed by using the same method as primary endpoint CR.

Survival data are collected at treatment and follow-up periods. Patients will be followed until death. Overall Survival (OS) is defined as the number of days from the date of randomization to the date of death. Kaplan-Meier methodology will be utilized.

Relapse-free survival (RFS) is defined as the time from the date of randomization to disease relapse, progression or death from MDS, whichever occurs first. If neither event occurs, RFS will be censored at the date of the last assessment. Kaplan-Meier methodology will be utilized.

Time to AML, OS and RFS will be analyzed using the similar methods as DOR.

Transition rate to SCT will be analyzed using the similar methods as complete response rate.

Important subgroup analyses will be detailed in the Statistical Analysis Plan.

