7.2.1 Screening (All patients)

All pre-treatment evaluations are to be performed within 28 days of Day 1 unless otherwise noted.

- Informed Consent
- TP53 mutation confirmation – send local report to vendor (see lab manual for instructions)
- Medical history – must include a thorough assessment and documentation of all transfusions received beginning from 8 weeks prior to randomization to end of treatment/off treatment; record transfusions on transfusion log.
- Physical examination
- Height
- Weight
- ECOG performance status
- Creatinine clearance (Cockcroft-Gault method; see [Appendix IV](#))
- Vital signs: including blood pressure, heart rate, respiration rate and temperature
- Hematology: hemoglobin, hematocrit, MCV, platelet count, blasts, WBC and WBC differentials.
- Blood chemistry including sodium, potassium, BUN, glucose, ALT/AST, alkaline phosphatase, total protein, total bilirubin, albumin, creatinine, calcium, chloride and magnesium.
- Serum pregnancy test: For patients with reproductive potential.
- ECG: Standard 12-lead ECGs to be performed with patient in a semi-recumbent position in triplicate.
- Concomitant medication
- Bone marrow aspirate and biopsy - Bone marrow assessment completed within 28 days of signing consent will be accepted to fulfill screening requirement as long as it has been completed following the last MDS treatment (excluding ESAs).
- Baseline bone marrow aspirate and biopsy core for exploratory objectives. If no aspirate is available, then peripheral blood is acceptable.
- Adverse Events: baseline, at the time of eligibility confirmation.

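### The CR test is valid and meets its stated power, but the plan leaves unused the baseline values on which CR is judged and gives no between-arm CR rate difference with an interval.

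*Combined protocol and SAP*

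**What the plan says.** Section 9.3.1 (Efficacy Analyses) states that "CR will be compared between treatment arms using a Cochran-Mantel-Haenszel (CMH) test stratified by age", and the synopsis says the same: "CR will be compared between arms using a Cochran-Mantel-Haenszel (CMH) test stratified by age". Each arm's CR rate is reported with an exact 95% interval. Between arms, "the treatment effect will be described using the CMH estimate of the common odds ratio" with its 95% interval. Age group is also the only randomisation factor (Sections 4.3 and 7.2.2).

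The sizing in Section 9.1 is on the rate scale. Its premise reads "If the true CR rate is 50% for the treatment arm and 25% for the control arm". With 77 patients per arm and two-sided testing at 0.05, the power claimed is 90%. The primary objective in Section 3.1 is also framed as a comparison of CR rates.

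Appendix II judges CR by fixed limits on marrow blasts, haemoglobin, platelets, neutrophils and peripheral blasts. Section 7.2.1 collects the matching values before treatment: "Hematology: hemoglobin, hematocrit, MCV, platelet count, blasts, WBC and WBC differentials", together with a marrow aspirate and biopsy.

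No covariate-adjusted analysis of CR is described, whether primary, supportive or sensitivity. Section 9.3.1 leaves only subgroup analyses to a separate Statistical Analysis Plan. Section 8.2.3 does adjust for baseline predictors and for blast, platelet and neutrophil counts, but only in the weighting method for stem cell transplant.

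**The concern.** CR is reached when several measured quantities cross fixed limits. How far a patient starts from those limits plausibly predicts whether they are crossed. Section 2.1 names marrow blast percentage and cytopenias as main drivers of overall prognosis, and Section 8.2.3 treats such counts as informative. If they predict CR, adjusting for them narrows the interval for the difference in CR rates, raises power without more patients, and corrects for chance imbalance in a trial of 154 that is stratified only by age.

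The second gap is the scale. A reader of the results will want the difference in CR rates with its interval, since that is what the trial was sized on. The plan gives two separate rates and an odds ratio. The two gaps are linked: covariate adjustment narrows the interval for a marginal quantity such as a rate difference. Adding covariates to an odds ratio model can raise power, but it changes what is estimated and does not narrow that interval.

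**Working it through.** **Inputs from Section 9.1.** CR 50% versus 25%, 77 per arm, two-sided alpha 0.05, power 90%.

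**Step 1: reproduce the stated figure** (two proportions, pooled variance under the null, no continuity correction).

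n per arm = [z(0.975)·√(2·0.375·0.625) + z(0.90)·√(0.50·0.50 + 0.25·0.75)]² / 0.25²
= [1.960·0.6847 + 1.2816·0.6614]² / 0.0625 = 76.7, so 77.

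Power at 77 = Φ[(0.25·√77 − 1.960·0.6847) / 0.6614] = Φ(1.288) = 90.1%. The plan's figure reproduces without any adjustment.

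**Step 2: effect of adjustment.** Let R² be the share of within-arm variance in CR explained by the baseline values. The documents give no value, so R² is an assumption and is shown as a range. Effective n per arm = 77/(1 − R²). The interval for the rate difference shrinks by √(1 − R²). Unadjusted, its half-width at the design rates is 1.960·√(0.4375/77) = 14.8 percentage points.

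| Assumed R² | Effective n per arm | CI width ratio | Power, 50% v 25% | Power, 45% v 25% |
|---|---|---|---|---|
| 0 | 77 | 1.00 | 90.1% | 74.4% |
| 0.05 | 81 | 0.97 | 91.5% | 76.6% |
| 0.10 | 86 | 0.95 | 92.9% | 78.8% |
| 0.20 | 96 | 0.89 | 95.3% | 83.4% |
| 0.30 | 110 | 0.84 | 97.4% | 88.0% |

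For R² from 0.05 to 0.30 the gain at the design rates is 1.4 to 7.3 points (91.5 − 90.1 and 97.4 − 90.1). That is equivalent to 4 to 33 more patients per arm. The half-width falls from 14.8 to 14.4 (14.8·0.975) or 12.4 (14.8·0.837). The 45% column is an illustration of a smaller effect, not a figure from the plan.

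**Step 3: simulation check of the formula.** 4,000 trials per setting, 77 per arm, age-stratified CMH against the standardised rate difference from a logistic model with arm, age stratum and four covariates. Assumptions: four independent normal covariates of equal weight, 70% aged 65 or over, age not prognostic, no missing data. The variance was scaled by 154/147 and referred to the normal distribution.

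| R² (AUC, control arm) | CMH | Standardised difference |
|---|---|---|
| 0 (0.50) | 90.3% | 89.7% |
| 0.04 (0.63) | 91.1% | 92.0% |
| 0.10 (0.70) | 90.9% | 93.5% |
| 0.19 (0.78) | 90.9% | 95.6% |
| 0.28 (0.83) | 91.0% | 97.3% |

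With both arms at 30% CR (3,000 trials per setting, Monte Carlo SE 0.4 points), null rejection was 4.1% to 5.1% for CMH and 5.0% to 6.1% for the standardised difference.

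**Step 4: does the gain survive a proper small-sample correction?** A second simulation (4,000 trials per setting, assumed prognostic strength) used a corrected SE:

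| Prognostic strength | CMH | Standardised, corrected | Change |
|---|---|---|---|
| None | 90.1% | 89.9% | −0.2 |
| Weak | 89.6% | 91.3% | +1.7 |
| Moderate | 90.8% | 94.1% | +3.3 |
| Strong | 90.7% | 96.6% | +5.9 |

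Null rejection there was 5.6% to 6.5% with the uncorrected robust SE, 4.9% to 5.8% after correction, and 4.4% to 5.1% for CMH. With uninformative covariates, the variance of the adjusted estimate rises by about 3%.

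**The case against.** The strongest reply is that nothing here is broken. The CMH test matches the randomisation, holds its level and meets its power target, so replacing it is largely a matter of preference. That stands, and it limits the point to an improvement.

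The second reply is that the size is assumed. A reader might infer from Section 2.1 that the documents show these values to predict CR. They do not: that section concerns overall prognosis. Section 2.2 reports a study in which TP53 mutation shortened survival under hypomethylating agents without affecting response rates, so the two should not be equated. The simulations also enter the covariates in their true form. A patient already at or below 5% blasts meets that component at entry, so a linear blast term may gain less. This stands as a limit on the magnitude, not on the direction.

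A reader might also infer that all four values are clean and complete in every patient. The documents do not support that. Blood may replace marrow when no aspirate is available (footnote i to the evaluation schedule), hydroxyurea is allowed up to randomisation (Section 6.3), and transfusions can move haemoglobin and platelets. Measurement noise in a baseline covariate does not bias a randomised comparison. It reduces the gain, and missing values need a rule.

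The third reply is that an uncorrected robust SE would exchange a test that holds its level for one that rejects about 6%. That is right, and any adjusted analysis must carry a correction.

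Lastly, the CR rate is reported in each arm, so the rate scale is not absent. What is missing is the between-arm difference and its interval. A separate Statistical Analysis Plan might supply both, but Section 9.3.1 assigns it only subgroups.

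**Conclusion.** The point holds as an efficiency improvement. It would be tempting to conclude that the primary analysis is wrong or underpowered, or that a known amount of precision is lost. The documents support neither conclusion: the test is valid, 90.1% power reproduces at 77 per arm, and no figure for prognostic strength is given.

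The documents do show that the values on which CR is judged are collected before treatment and used in no CR analysis, and that no rate difference with an interval is planned although the objective and the sizing are in rates. Under an assumed R² of 0.05 to 0.30, adjustment would add about 1 to 7 points of power at 50% versus 25%. If the covariates carry no information, the cost is under 1 point. The benefit would matter most if the true effect were smaller than assumed: at 45% versus 25%, an R² of 0.20 would take power from 74.4% to 83.4%. These results also assume no missing baseline data and a reasonably specified model.

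**What to change.** Amend Section 9.3.1 and the matching synopsis text before any outcome data are reviewed. The timing matters because the trial is open label.

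- Prespecify the standardised difference in CR rate between arms, with 95% CI, in the ITT population. Take it from a logistic model with arm, age stratum, and baseline haemoglobin, platelets, ANC and marrow blast percentage as continuous terms.
- Use a robust SE with a small-sample correction and a t reference, or take the p-value from a re-randomisation test within age strata. The second option is the safer for the level, since corrected rejection still ranged from 4.9% to 5.8%.
- State a simple imputation rule for missing baseline values, for example marrow blasts when no aspirate is available.
- Report the age-stratified CMH test and common odds ratio alongside, and state in advance which analysis supplies the primary p-value.

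The sample size and the stated power stay as they are. The cost is analysis wording, the imputation rule and a short check of the test's level. It needs no extra patients, visits or measurements.
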